4.5 Summary of Clinical Data

ARDIFF

RDY

One Phase I FTIH study (D8850C00001) and 3 Phase III studies (D8850C00002 [PROVENT; pre-exposure prophylaxis], D8850C00003 [STORM CHASER; post-exposure prophylaxis], and D8851C00001 [TACKLE; treatment of COVID-19]) in adults are ongoing with AZD7442. In addition, participation in 3 externally-sponsored platform studies (ACTIV-2 and ACTIV-3 [sponsored by NIAID] and DisCoVeRy [sponsored by Inserm]) are ongoing with AZD7442.

AZD7442 has been found to prevent symptomatic SARS-CoV-2 infection in the PROVENT study. The PROVENT study is phase III double-blind placebo-controlled study of AZD7442 for pre-exposure prophylaxis of SARS-CoV-2 in adults. In the PROVENT study a total of 5197 participants were randomized and dosed in a 2:1 ratio to receive a single dose (x 2 IM injections) of either AZD7442 300 mg (N = 3460) given as two sequential IM injections of AZD8895 and AZD1061 (one in each gluteal region), or corresponding placebo on Day 1. Randomization was stratified into two cohorts: Cohort 1: Adults \geq 60 years of age. All such participants were considered as being at increased risk for inadequate response to active immunization on the basis of age (presumed immunosenescence). Cohort 1 was capped, not to exceed 80% of total participants randomized. Within this cohort, randomization was stratified by residence in a long-term care facility or not. Cohort 2: Adults < 60 years of age. Cohort 2 was capped, not to exceed 80% of total participants randomized. Within this cohort, randomization was stratified by risk of exposure to infection with SARS-CoV-2.

As of the primary analysis data cut-off of 05 May 2021, randomization was complete, 5254 participants (3500 AZD7442 and 1754 placebo) had been randomized, 5109 (97.2%) (3409 [97.4%] AZD7442 and 1700 [96.9%] placebo) were ongoing in the study, and 145 (2.8%) participants (91 [2.6%] AZD7442 and 54 [3.1%] placebo) had discontinued the study. The mean age of participants was 53.5 years. Most participants were White (3794 [73.0%]), 899 (17.3%) were Black or African American, and 170 (3.3%) were Asian. A slightly higher proportion of participants were male (53.9%) than female (46.1%).

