The primary outcome measures of PROVENT were the incidence of the first case of SARS CoV-2 RT PCR positive symptomatic illness [Time Frame: Day 183] and to estimate the efficacy of a single IM dose of AZD7442 compared to placebo for the prevention of SARS-COV-2 prior to Day 183, and to assess the safety and tolerability of a single IM dose of AZD7442 compared to placebo.

Positive high-level results from PROVENT showed that AZD7442, reduced the risk of developing symptomatic SARS-CoV-2 by 77% (95% confidence interval (CI): 46, 90), when compared to placebo. There were no cases of severe SARS-CoV-2 or SARS-CoV-2-related deaths in those treated with AZD7442. In the placebo arm, there were three cases of severe SARS-CoV-2, which included two deaths. AZD7442 was well tolerated and preliminary analyses show adverse events were similar between the placebo and AZD7442 groups (https://www.astrazeneca.com/media-centre/press-releases/2021/azd7442-prophylaxis-trial-met-primary-endpoint.html).

More than 75% of participants had co-morbidities, which include conditions that have been reported to cause a reduced immune response to vaccination. Approximately 43% of participants were 60 years and over. In addition, more than 75% had baseline co-morbidities and other characteristics that are associated with an increased risk for severe SARS-CoV-2 should they become infected, including those with immunosuppressive disease or taking immunosuppressive medications, diabetes, severe obesity

RAPID-PROTECTION Protocol v.5.0 09/05/2023

or cardiac disease, chronic obstructive pulmonary disease, chronic kidney and chronic liver disease. The results from PROVENT show that AZD7442 can prevent SARS-CoV-2 in symptomatic high-risk populations. However, within the PROVENT study, there were limited numbers of patients at the highest risk of developing SARS-CoV-2, and all of the study participants were unvaccinated against SARS-CoV-2.

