Importantly, AZD7442 reaches therapeutic levels within 4 hours of IM injection, whereas SARS-CoV2 vaccines takes up to two doses given 12 weeks apart to induce maximum protection against the infection. Therefore, giving AZD7442 could potentially induce rapid protection in patients undergoing procedures like haematological stem cell transplantation, whilst their adaptive immunity recovers after their transplantation to allow them to respond to vaccination.

The PROVENT study recruited patients that were not vaccinated against SARS-CoV-2, and since PROVENT completed enrolment, SARS-CoV-2 vaccinations have been widely administered around the world. Although it is known that booster doses of SARS-CoV-2 vaccines enhance SARS-CoV-2 immunity in healthy volunteers (Flaxman et al, 2021), it is not known if the same applies to patients with impaired immunity that have had previous SARS-CoV-2 vaccinations/boosters (https://www.gov.uk/government/news/jcvi-issues-interim-advice-on-covid-19-booster-vaccination).

At the present time, there are no clinical studies which have evaluated the safety or immunogenicity of AZD7442 given in combination with SARS-CoV-2 vaccination boosters. PROVENT only included a small subset of patients with highly immunosuppressive conditions.

Therefore, additional clinical studies are required to further delineate the immunological effects of giving AZD7442 to patients with immunosuppressive conditions either alone or followed by vaccination as a standard of care treatment. These studies will also confirm that the protective effect of AZD7442 is maintained against SARS-CoV-2 over the 12-month period between injection and whether booster vaccinations further enhance immune protection through enhanced humoral and cellular responses against SARS-CoV-2 after previous vaccination against SARS-CoV-2 and whether the combination is safe in highly immunosuppressed patients.

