4.7.1 Hypotheses to be tested

1) That treatment with AZD7442 in combination with a SARS-CoV-2 vaccine is safe and well tolerated,

2) That vaccination with a SARS-CoV-2 vaccine does not reduce AZD7442 titres in humans and

3) That AZD7442 in combination with a SARS-CoV-2 vaccine enhances immune responses to SARS-CoV-2.

5 Trial objectives/endpoints and outcome measures

We propose to test the following objectives:

Table 1: Objectives and outcome measures

	Objectives	Outcome measures
Co-Primary	To assess the pharmacokinetics of AZD7442 administered as a single dose of 600 mg IM in immunosuppressed patients	Serum samples will be taken at Day 0 (Predose AZD7442), and days 28, 112 and 180 post AZD7442 treatment and samples shipped to an AstraZeneca approved laboratory for Pharmacokinetics (PK) analysis.
		Samples collected for analyses of AZD7442 serum concentration may also be used to evaluate safety or efficacy aspects related to concerns arising during or after the trial. PK results from the trial will be compared to results from other phase III studies with AZD7442 such as PROVENT.
	To assess the safety and tolerability of a single IM dose of AZD7442, followed by SARS-CoV2 vaccine booster 28 days later with reference to serious adverse events (SAEs) in highly vulnerable patients.	SAE reporting throughout the trial using CTCAE V5.0
	To assess the SARS-CoV-2 specific humoral and cellular immune response against SARS-CoV-2 variants, when a SARS-CoV-2 vaccine is administered 28 days after AZD7442 in patients who are immune suppressed.	The function and magnitude of SARS-CoV-2 specific antibody and T cell responses will be measured at baseline and at additional multiple timepoints after the administration of AZD7442.
		Assays will quantify the amount of serum antibodies to the spike (S) and the nucleocapsid (N) antigens of SARS-CoV-2. This assay will enable the discrimination of antibody responses to SARS-CoV-2 that results from vaccination and/or SARS-CoV- 2 infection. Ab function, including viral neutralisation will be assessed.

		The magnitude and function of SARS-CoV-2 specific T cell responses following the booster vaccination will use assays that give insight into T cell function. Laboratories will measure neutralizing antibodies to SARS-CoV-2 using validated wild-type neutralization assay or pseudo- neutralization assays.

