11.1 Dosing schedule

IMP	Dose	Route	Time point
AZD7442 (AZD8895	600 mg single dose of AZD7442	IM injection	Day 0
followed by AZD1061)	(300 mg of AZD8895 and 300 mg of AZD1061)		
Comirnaty bivalent	0.3ml containing 15 micrograms of	As per SPC	Day 28
Original/Omicron	tozinameran and 15 micrograms of		(after day 28
BA.1: Arm 1	riltozinameran, a COVID-19 mRNA Vaccine		bloods have
	(embedded in lipid nanoparticles)		been taken)
Spikevax bivalent	Spikevax: 0.5ml containing 25 micrograms of	As per SPC	Day 28
(Original/Omicron):	elasomeran and 25 micrograms of		(after day 28
Arm 2	imelasomeran, a COVID-19 mRNA Vaccine		bloods have
	(embedded in lipid nanoparticles).		been taken)

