15.3 Sample size

We aim to recruit a total of 350 patients with immunosuppressive conditions. Sample sizes required for analysis of the various groups and outcomes have been based on SARS-COVID-2 IgG responses taken from the analysis of the PROVENT trial and other similar trials.

To compare Groups 1 + 2 + 3 + 4 with healthy volunteers from the PROVENT trial to show a reduction in IgG levels at 90% power with a 5% significance of 0.5 (log domain) and SD of 1 we need 70 patients. We expect this consideration to show that the variance in IgG levels is larger than healthy volunteers and have therefore powered to allow for the same comparison in each of the four sub-groups (1, 2, 3, 4) – 70 per group to give a total of 280 required. Allowing for loss to follow-up of 20% we will aim to recruit 350 patients stratified across the selected groups. To maximise heterogeneity at the group level and improve branching decisions, we will target even recruitment numbers in the subgroups of each group (level 3 in figure 2).

Analysis of the identified groups 1 + 2 + 3 + 4 will be undertaken once 280 completed datasets at 28 days have been achieved. If the variance in IgG levels is shown to be significantly different to healthy controls or more variable, then the analysis will progress to groups 1, 2, 3, and 4 individually and recruitment targets re-estimated.

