16.1 Main analysis

16.1.1 Immunogenicity at 28 days following administration of AZD7442

The function and magnitude of SARS-CoV-2 specific antibody and T cell responses will be measured at baseline and at additional multiple timepoints after the administration of AZD7442. The immunological effect of the study interventions will be determined by comparison of the results of immunological assessments at baseline and subsequent time points.

Assays will quantify the amount of serum antibodies to the spike (S) and the nucleocapsid (N) antigens of SARS-CoV-2. This assay will enable the discrimination of antibody responses to SARS-CoV-2 that results from vaccination and/or SARS-CoV-2 infection. Ab function, including viral neutralisation will be assessed.

The magnitude and function of SARS-CoV-2 specific T cell responses following the booster vaccination will use assays that give insight into T cell function. Laboratories will measure neutralizing antibodies to SARS-CoV-2 using validated wild-type neutralization assay or pseudo-neutralization assays.

Comparisons of immunogenicity outcomes will be made with age and gender matched healthy controls from the PROVENT III trial. Group data will be requested from the PROVENT trial. Values will be log-transformed and mean and standard deviation calculated for the same groups at each timepoint. The PROVENT data will be used to calculate the overall standard deviation of a population with the same age / sex distribution as each of our cohorts at each timepoint. The mean and standard

deviation and its 95% confidence interval will be calculated for each cohort for comparison with the PROVENT data at each timepoint.

The ratio of the variances in the log transformed domain will be tested to assess if it is significantly different from 1. All tests will be one sided and focussed on if the trial patients perform less well than the healthy volunteers in terms of response to vaccine. Results will be reported as the ratio of variances, 95% confidence intervals and p values.

16.1.2 Immunogenicity at 28 days following administration of AZD7442 followed by a SARS-CoV-2 vaccine 28 days later (outcome measured at day 56)

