To assess if treatment with AZD7442 followed by a SARS-CoV-2 vaccine 28 days later will increase levels of anti-SARS-COVID-2-anti S-RBD neutralising antibodies in patients. This will be assessed in a hierarchical way firstly comparing age-matched healthy controls from the PROVENT III trial of the AZD7442 and AZD1222 all patients (groups 1, 2, 3 and 4) on both point estimator and variance and if the variance is greater than subdividing into the individual groups by patient group.

Comparisons will be made between each of the vaccines using an ANCOVA model with baseline value as a covariate. An exploratory analysis will be conducted to examine differences between the vaccine types and patient cohorts (see section 16.3 below).

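### Mean antibody and PK comparisons with PROVENT ignore a twofold difference in AZD7442 amount, and the Day 56 comparator in 16.1.2 conflicts with the protocol's own account of PROVENT

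*Protocol*

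**What the plan says.** - **Comparator at Day 28.** Section 16.1.1: "Comparisons of immunogenicity outcomes will be made with age and gender matched healthy controls from the PROVENT III trial". Means and SDs of log values are set beside PROVENT at each timepoint. The formal test is on the ratio of log variances, and all tests are one-sided towards patients doing worse.
- **Sample size.** Section 15.3 seeks, against PROVENT healthy volunteers, a "reduction in IgG levels at 90% power with a 5% significance of 0.5 (log domain) and SD of 1". This gives 70 patients, 280 over four groups, and 350 after 20% loss.
- **Comparator at Day 56.** Section 16.1.2 proceeds hierarchically, "firstly comparing age-matched healthy controls from the PROVENT III trial of the AZD7442 and AZD1222 all patients", on both point estimator and variance.
- **PK.** Section 5, Table 1: "PK results from the trial will be compared to results from other phase III studies with AZD7442 such as PROVENT".
- **What PROVENT was.** Section 4.5 describes a placebo-controlled trial of "AZD7442 300 mg (N = 3460) given as two sequential IM injections of AZD8895 and AZD1061". It adds that "all of the study participants were unvaccinated against SARS-CoV-2" and that more than 75% had co-morbidities.
- **What this trial is.** Section 11.1: "600 mg single dose of AZD7442". Section 8.1 requires completed SARS-CoV-2 vaccination before entry.
- **Combination data.** Section 4.6.4: "there are no clinical studies which have evaluated the safety or immunogenicity of AZD7442 given in combination with SARS-CoV-2 vaccination boosters".

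**The concern.** After dosing, much of the anti-spike IgG and neutralising activity in serum is AZD7442 itself, so the amount given feeds directly into the outcome. Patients here received twice PROVENT's amount and may also carry antibody from earlier vaccination. Both raise the trial mean, while the one-sided question is whether that mean is lower. Matching on age and sex removes neither. Calling the PROVENT group healthy also sits badly with its co-morbidity.

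A real deficit in immunosuppressed patients could therefore be hidden in the mean contrast that justifies the sample size. Section 6 allows a cohort to be closed if immunogenicity looks good. If that judgement draws on the mean contrast, a deficient cohort could look adequate. The descriptive PK comparison in Table 1 has the same dose mismatch.

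At Day 56 the problem is one of consistency: section 16.1.2 attributes to PROVENT a vaccine component that the rest of the protocol says it did not have.

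**Working it through.** **1. Reproduce the 70.** Inputs from section 15.3: difference 0.5, SD 1, 5% significance, 90% power. Sidedness is not stated there; section 16.1.1 makes all tests one-sided.

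n per group = 2(1.645 + 1.282)² / 0.5² = 68.5, so 69; the t-based version gives 70. The two-sided version gives 85 (t: 86) and one-sample versions give 35 or 43. The stated 70 is therefore a one-sided comparison of 70 v 70. Also 4 × 70 = 280 and 280/0.8 = 350. The arithmetic is right.

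Standard error at 70 v 70 = √(2/70) = 0.169. Power = Φ(0.5/0.169 − 1.645) = 90.5%.

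**2. How levels scale with dose.** Section 4.6 reports exposure linear in dose for IV administration only. It also gives neutralising-titre fold differences of 3000 mg over 1000 mg and over 300 mg IV. Their quotient is the 1000 v 300 mg ratio, a 3.33-fold dose step. The exponent is b = ln(titre ratio)/ln(3.33).

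- 7 days: 16.1/3.5 = 4.6-fold, b = 1.27
- 150 days: 9.0/2.7 = 3.3-fold, b = 1.00
- 210 days: 10.4/4.3 = 2.4-fold, b = 0.73

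These values bracket proportionality (b = 1). They are IV titres, so using them for IM dosing and for an IgG assay is an assumption.

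**3. Effect on the mean contrast.** Doubling the dose adds b × log 2 to the trial mean. Apparent deficit = 0.5 − b × log 2. Power = Φ(apparent deficit/0.169 − 1.645). The log base is not stated, so both are shown.

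| b | Natural log: offset, apparent deficit, power | Log10: offset, apparent deficit, power |
|---|---|---|
| 0 | 0, 0.50, 90.5% | 0, 0.50, 90.5% |
| 0.5 | 0.35, 0.15, 23% | 0.15, 0.35, 66% |
| 0.73 | 0.51, −0.01, 4.5% | 0.22, 0.28, 50% |
| 1 | 0.69, −0.19, 0.3% | 0.30, 0.20, 32% |
| 1.27 | 0.88, −0.38, under 0.1% | 0.38, 0.12, 17% |

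At b = 1, larger groups help on log10: 76% at 280 v 280, 50% at 70 v 3460, and 433 per group for 90%. On the natural log the sign is reversed, so no sample size helps. Keeping 90% power at 70 v 70 would need a true deficit of 0.5 + 0.69 = 1.19 (natural log) or 0.5 + 0.30 = 0.80 (log10).

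**4. Effect on the variance ratio.** If every level is multiplied by 2^b, each log value shifts by the same constant and the log variance does not change. The formal test in section 16.1.1 is therefore untouched by a purely multiplicative dose effect. Differences in vaccination history or co-morbidity could still alter the variance; the documents give no figures for this.

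**5. Day 56, set side by side.** Section 4.5 describes PROVENT as AZD7442 against placebo in unvaccinated people. Section 4.6.4 says that no clinical study has evaluated AZD7442 with a booster. Section 16.1.2 describes PROVENT as a trial of AZD7442 and AZD1222. Nor is AZD1222 one of the two boosters in sections 9.5 and 11.1. These statements cannot all hold.

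**6. Decay between Day 28 and Day 56.** With the half-life of about 90 days in section 4.6, 2^(−28/90) = 0.81. This is a fall of about 19%, or −0.22 on the natural log, before any booster effect.

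**The case against.** The strongest reply is that the test section 16.1.1 actually specifies is on variances, where dose cancels. That stands, and it confines the power figures to the mean contrast. It does not dispose of the point: section 15.3 is powered on a mean difference, section 16.1.1 sets means beside PROVENT, and sections 6 and 16.1.2 call for comparison on the point estimator as well as the variance.

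Second, the loss depends on the log base and on IM proportionality, neither of which is given. That also stands, so a range is shown rather than one figure. Even half the offset on the log scale leaves 23% or 66%.

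Third, more than 75% with co-morbidities leaves up to about a quarter of PROVENT without (0.25 × 3460 = 865 if the arms are alike), and healthy controls may mean that subset. Section 4.6.4 says that few PROVENT participants were highly immunosuppressed, and no effect of co-morbidity on AZD7442 levels is shown. This is fair. The complaint is that the stated matching, on age and sex, does not select such a subset.

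Fourth, adjustment methods may sit in the SAP. They may, and their absence from the protocol is not the finding. The finding is that the comparator and the power statement, as fixed in the protocol, do not fit its own description of PROVENT.

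Fifth, sections 4.7 and 6 mention other trials of AZD7442 and of vaccines, so section 16.1.2 may be a garbled reference to separate control sources. That is possible, but the section names only PROVENT.

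**Conclusion.** The point holds for comparisons of means and PK with PROVENT. Under full dose proportionality, a planned deficit of 0.5 appears as an excess of 0.19 on the natural log (power 0.3%) or a deficit of 0.20 on log10 (power 32%; 76% at 280 v 280). Over exponents of 0.73 to 1.27 the power is 4.5% to under 0.1%, or 50% to 17%. These figures rest on carrying IV dose scaling over to IM dosing and to the IgG assay, and on an unstated log base. They do not include prior vaccination, which probably adds to the masking but cannot be sized from the protocol.

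The Day 56 comparator is an internal contradiction and needs no calculation.

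A reader might go further and infer that all three co-primary aims on PK, immune response and vaccine effect on titres fail, or that the Day 56 analysis cannot be run. The protocol does not support either. The outcome for the vaccine's effect on AZD7442 titres names no PROVENT comparison. The PK comparison is descriptive and not limited to PROVENT. The immune-response aim also rests on change from baseline, and the randomised ANCOVA between vaccines in section 16.1.2 can run as written.

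**What to change.** 1. **Means and PK.** In sections 15.3, 16.1.1, 16.1.2 and Table 1, make mean and PK comparisons with PROVENT on dose-normalised values, or scale the PROVENT reference mean by the dose ratio. Add a sensitivity analysis over departures from proportionality, for example exponents of 0.73 to 1.27. State the log base, and state that the power in section 15.3 refers to the dose-normalised contrast. Cost: one added, openly stated assumption.
2. **Control group.** Request PROVENT AZD7442-arm summaries that exclude participants with immunosuppressive disease or medication. Call the group healthy only if co-morbid participants are also excluded. Report the difference in prior vaccination as a limitation. Cost: a modified request for aggregate data and fewer controls.
3. **Day 56.** Remove the PROVENT/AZD1222 comparator from section 16.1.2. Assess the booster by within-participant change from Day 28 to Day 56, allowing for AZD7442 decay (about 19%). One way is to compare it with the same-interval ratio in unvaccinated PROVENT participants, in which dose cancels under linear kinetics. This needs suitable PROVENT sampling days, which the protocol does not give. Base the decision to subdivide groups on the variance comparison, so that removing the comparator does not also remove the trigger.
4. **Consistency.** Reconcile sections 4.5, 4.6.4, 4.7, 6, 15.3, 16.1.1 and 16.1.2 on who the comparator is and what it received. No view is taken on the dose.

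All of this is wording, analysis and one data request; no trial procedure changes.

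### The plan sets out to show that AZD7442 followed by a vaccine increases patients' immune responses, but the comparison it specifies, against healthy controls, cannot show an increase

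*Protocol*

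**What the plan says.** **The question.** Hypothesis 3 in Section 4.7.1 reads "That AZD7442 in combination with a SARS-CoV-2 vaccine enhances immune responses to SARS-CoV-2". Section 16.1.2, for the day 56 outcome, asks whether AZD7442 followed 28 days later by a vaccine "will increase levels of anti-SARS-COVID-2-anti S-RBD neutralising antibodies in patients".

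**The method for that question.** Section 16.1.2 continues: "This will be assessed in a hierarchical way firstly comparing age-matched healthy controls from the PROVENT III trial". All patients are compared with these controls on both point estimate and variance, and then by patient group if the variance is greater. It states no direction and no sidedness. It adds an ANCOVA comparing the two boosters with each other.

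**The test direction.** Section 16.1.1, headed as the day 28 analysis, says "The ratio of the variances in the log transformed domain will be tested to assess if it is significantly different from 1". The next sentence makes every test "one sided and focussed on if the trial patients perform less well than the healthy volunteers in terms of response to vaccine". Section 15.3 sizes the trial to show a reduction in IgG of 0.5 (log scale, SD 1) against PROVENT volunteers, with 90% power at 5% significance: 70 per group, 280 in total, 350 after 20% loss.

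**A baseline comparison.** Section 16.1.1 also says the effect of the interventions will be judged by comparing baseline with later time points. Sections 12 and 13.1 place that baseline before AZD7442.

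**The concern.** An increase in patients is a change within patients. A comparison with healthy people measures how far patients stand from them. The two differ in population and, given the stated direction, in sign. A significant result would show that patients remain below healthy volunteers, which is not evidence that the vaccine raised anything. A non-significant result would be expected both where the vaccine closed a deficit and where there was never a deficit. Followed as written, the method for the Section 16.1.2 aim leaves the vaccine-related increase without a test. A matched, perfectly comparable control group would not cure this.

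**Working it through.** **1. The plan's own sample size.** Inputs from Section 15.3: difference 0.5, SD 1, 5% significance, 90% power.
- Two-sample, one-sided: n = 2 × (1.645 + 1.282)² / 0.5² = 68.5, so 69 per group. The t version reaches 90% at 70. This reproduces the stated 70.
- Two-sample, two-sided: 85. One-sample: 35 one-sided, 43 two-sided. None of these gives 70.
- 280 / (1 − 0.20) = 350, as stated.

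Among these variants, 70 matches only a one-sided two-sample test, and the stated effect is a reduction.

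**2. A mean comparison in the stated direction.** Assume 70 per group in both groups (the protocol gives no control number) and SD 1. SE = √(2/70) = 0.169. With d = patients minus controls, P(reject) = Φ(−d/SE − 1.645).

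| d (log) | P(reject) |
|---|---|
| −0.5 | 90.5% |
| −0.25 | 43.4% |
| 0 | 5.0% |
| +0.25 | 0.09% |
| +0.5 | 0.0002% |

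If patients start 0.5 below controls (an assumption), a booster that adds nothing gives 90.5% and one that closes the gap gives 5.0%. If they start level, a booster that adds nothing gives 5.0%.

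**3. The variance ratio.** This is the statistic Section 16.1.1 names. One-sided 5% F test for larger variance in patients, 10,000 simulated trials per case, SD 1 before any gain:

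| Booster effect | 70 v 70 | 280 v 280 |
|---|---|---|
| Adds nothing | 4.8% | 5.1% |
| Adds 0.5 to everyone | 4.8% | 5.2% |
| Adds 1 to half | 22.5% | 59% |
| Adds 1.5 to half | 58% | 98% |
| Adds 2 to half | 91% | about 100% |

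A uniform gain is invisible. A gain in only some patients widens the spread and would count as performing less well.

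**4. The other stated comparisons.** All participants receive a booster (Section 6), so the ANCOVA can separate the two boosters but cannot show that boosting adds anything. A change from baseline to day 56 spans both AZD7442 and the vaccine, so it mixes infused antibody with any vaccine effect.

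**5. A within-patient alternative.** Day 28 blood is drawn before the booster (Sections 11.1 and 13.1) and day 56 blood is scheduled. For n = 70 pairs and a rise of 0.5, SD of change = √(2(1 − ρ)), SE = SD/√70, and two-sided 5% power = Φ((0.5 − decay)/SE − 1.96). The within-patient correlation ρ is assumed; the protocol gives none.

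Section 4.6 gives a half-life of about 90 days. Decay over 28 days is 1 − 2^(−28/90) = 19%, which is 0.216 on natural log or 0.094 on log10. Section 15.3 does not give the log base.

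| ρ | No decay deducted | Natural log, full deduction | Log10, full deduction |
|---|---|---|---|
| 0.3 | 94% | 52% | 82% |
| 0.5 | 99% | 66% | 93% |
| 0.8 | >99.9% | 96% | >99.9% |

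**The case against.** **The one-sided sentence belongs to another analysis.** It sits in the day 28 section, between sentences about the variance ratio, and day 28 blood precedes the trial booster. This stands in part. Extending it to day 56 rests on its reference to all tests and to response to vaccine, and on that section's comparisons at each time point. The main point does not depend on the extension: without it, Section 16.1.2 still answers a question about increase with a comparison to healthy controls.

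**The baseline comparison already covers a rise, and its test can be left to the SAP.** The missing test, direction and significance level are indeed no fault in a protocol. The comparison could show that levels rose over the whole combined course. It cannot isolate the vaccine's contribution, and Section 16.1.2 does not assign the aim to it.

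**Stronger readings.** A reader might infer that the tests reject most often when the vaccine adds nothing. That holds only for a mean comparison in which patients start below controls. It is wrong for the variance ratio, where an uneven benefit raises rejection. A reader might also infer that the trial cannot address hypothesis 3 at all. The documents do not support this: the needed samples are collected, and the fault lies in the stated method.

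**The paired test is not clean either.** There is no unboosted arm, and the change is measured on a background of infused antibody. Section 4.6 reports titres 10 to 15 times those of convalescent plasma at day 91 after 300 mg. This stands and must be stated with the result.

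**Conclusion.** The concern holds in this form: the stated aim is an increase in patients, the stated method is a comparison with healthy controls, and the only stated direction is that patients do worse. Neither the mean comparison nor the variance ratio can show an increase. Under the stated direction, power to find patients above controls is effectively nil. The rejection rates assume SD 1, equal groups of 70, normality and, for day 56, that the Section 16.1.1 direction applies. The 0.5 is the protocol's planning value for IgG, not a stated post-booster deficit in neutralising antibody. This should be corrected because, followed as written, the plan would leave the vaccine's contribution to hypothesis 3 untested.

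**What to change.** In Section 16.1.2, assess the vaccine-related increase by the within-patient change in log value from day 28 (pre-booster) to day 56, with a two-sided 95% confidence interval, and claim an increase only if the lower bound is above 0. In Section 16.1.1, confine the one-sided rule to the healthy-volunteer comparison, and label that comparison, there and in Section 16.1.2, as the remaining gap to healthy people.

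The cost is protocol and SAP wording; no new samples or visits are needed. State three limits beside the result:
- With no unboosted arm, the change is uncontrolled.
- For anti-spike and neutralisation read-outs, decay of infused antibody of up to about 19% over the interval works against showing a rise.
- Power at 70 pairs for a rise of 0.5 depends on the log base and on the correlation. For ρ from 0.3 to 0.8 it is about 52% to 96% on natural log and 82% to over 99.9% on log10 with decay deducted in full, so the log base should be stated.
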